## 1 STUDY DETAILS

This is the statistical analysis plan (SAP) for study D5290C00008. The SAP expands on the statistical analyses specified in the clinical study protocol (CSP). Any changes to any specifications in the CSP will be described in Section 6 of this document.

This SAP is based on the CSP Amendment Version 3.0, dated 23 June 2021 (global amendment), and 4 July 2021 (Japan amendment).

### 1.1 Study objectives

The study objectives are to evaluate the safety and tolerability, pharmacokinetics (PK), occurrence of anti-drug antibody (ADA) and efficacy for nirsevimab in immunocompromised children  $\leq$  24 months of age.

#### 1.1.1 Primary objective

The primary objective is to evaluate the safety and tolerability of nirsevimab when administered to immunocompromised children  $\leq$  24 months of age.

#### 1.1.2 Secondary objectives

[figure not shown]
The secondary objectives are:

- To evaluate the PK of nirsevimab.
- To evaluate the ADA responses to nirsevimab in serum.
- To assess the efficacy of nirsevimab when administered as a single intramuscular (IM) dose to infants  $\leq$  24 months of age.

#### 1.1.3 Exploratory objectives

The exploratory objectives are:

CCI

- To assess healthcare resource utilization (HRU) for nirsevimab recipients.

[figure not shown]
### 1.2 Study design

This is a Phase 2, open-label, uncontrolled single-dose study to assess the safety and tolerability, PK, occurrence of ADA, and efficacy of nirsevimab in immunocompromised children who are  $\leq$  24 months of age at the time of dose administration. The study is planned to be conducted in South Africa, the United States, and the European Union, in addition to Japan, where enrolment in the study originated. Approximately 100 subjects will be enrolled. Due to atypical RSV circulation and RSV seasons in 2020/2021, the RSV season will not be

considered for dose selection. The dose of nirsevimab is administered only based on the age and body weight regardless of the first or second RSV season subjects is entering. Subjects who are in their first year of life at the time of dose administration will receive nirsevimab as a single, fixed IM dose of 50 mg if body weight  $< 5$  kg or 100 mg if body weight  $\geq 5$  kg. Subjects in their second year of life at the time of dose administration will receive nirsevimab as a single, fixed IM dose of 200 mg. Subjects will be followed up for approximately 1 year after dose administration.

A flow diagram of the study design is presented in [Figure 1](#).

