3.1.2 Treatment Regimen

As this is a single-arm study, all subjects will receive nirsevimab. Subjects who are in their first year of life AND entering their first RSV season at the time of dose administration will receive nirsevimab as a single, fixed IM dose of 50 mg if body weight < 5 kg or 100 mg if body weight ≥ 5 kg ($n = \sim 50$). Subjects in their second year of life AND entering their second RSV season at the time of dose administration will receive nirsevimab as a single, fixed IM dose of 200 mg ($n = \sim 50$).

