4.1.2 Inclusion Criteria

Subjects must meet all of the following criteria:

1. Neonate, infant, or young child \leq 24 months of age who, per Investigator judgment, are:
 - (a) In their first year of life AND entering their first RSV season at the time of dose administration

OR

- (b) In their second year of life AND entering their second RSV season at the time of dose administration
2. The subject must meet at least 1 of the following conditions at the time of informed consent.
 - (a) Diagnosed with combined immunodeficiency (severe combined immunodeficiency, X-linked hyper-immunoglobulin M [IgM] syndrome, etc); antibody deficiency (X-linked agammaglobulinemia, common variable immunodeficiency, non-X-linked hyper-IgM syndromes, etc); or other immunodeficiency (Wiskott-Aldrich syndrome, DiGeorge syndrome, etc), or
 - (b) Diagnosed with human immunodeficiency virus infection, or
 - (c) History of organ or bone marrow transplantation, or
 - (d) Subject is receiving immunosuppressive chemotherapy, or
 - (e) Subject is receiving systemic high-dose corticosteroid therapy (prednisone equivalents ≥ 0.5 mg/kg every other day, other than inhaler or topical use), or
 - (f) Subject is receiving other immunosuppressive therapy (eg, azathioprine, methotrexate, mizoribine, mycophenolate mofetil, cyclophosphamide, cyclosporine, tacrolimus, cytokine inhibitors, etc)

All efforts will be made to recruit subjects for representation across all the immunocompromised conditions indicated in inclusion criteria (a) - (f).

3. Written informed consent and any locally required authorization obtained from the subject's parent(s)/legal representative(s) prior to performing any protocol-related procedures, including screening evaluations.
4. Subject's parent(s)/legal representative(s) able to understand and comply with the requirements of the protocol including follow-up visits as judged by the Investigator.
5. Subject is available to complete the follow-up period, which will be approximately 1 year after receipt of nirsevimab.

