4.1.4 Subject Enrollment and Randomization

Study participation begins (ie, a subject is “enrolled”) once written informed consent is obtained. Once informed consent is obtained, a subject identification (SID) number will be assigned, and the screening evaluations may begin to assess study eligibility (inclusion/exclusion) criteria. The SID number will be used to identify the subject during the screening process and throughout study participation, if applicable.

A master log of all consented subjects will be maintained at the site and will document all screening failures (ie, subjects who are consented but do not meet study eligibility criteria), including the reason(s) for screening failure.

Subjects who fail to meet the inclusion/exclusion criteria (ie, screening failures) should not receive investigational product. The Investigator must consult with the Sponsor before a subject who has failed screening may be considered for rescreening.

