4.1.6 Discontinuation of Investigational Product

Each subject will receive a single IM dose of investigational product. An individual subject will not receive investigational product if any of the following occur in the subject in question:

- Withdrawal of consent
- Subject is determined to have met one or more of the exclusion criteria or failed to meet all of the inclusion criteria for study participation

Subjects who have received any investigational product will be followed for protocol-specified assessments including follow-up of any AEs unless consent is withdrawn specifically from further study participation (Section 4.1.5) or the subject is lost to follow-up. Subjects who have not received investigational product, regardless of reason, will not be followed.

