4.5.1.2 Dose Preparation Steps and Treatment Administration

No incompatibilities between nirsevimab and polycarbonate or polypropylene syringes have been observed.

Nirsevimab does not contain preservatives and any unused portion must be discarded. Total in-use storage time from needle puncture of the investigational product vial to start of administration should not exceed 4 hours at room temperature. If storage time exceeds these limits, a new vial should be used.

The dose administration steps are as follows:

1. Infants in the first year of life and entering their first RSV season at time of dosing

(a) Infants < 5 kg body weight at time of dosing:

A dose of 50 mg (ie, 0.5 mL) nirsevimab will be obtained by withdrawing the entire contents of 1 investigational product vial with an appropriately sized syringe, and administered as 1 single (ie, 0.5 mL) injection.

(b) Infants ≥ 5 kg body weight at time of dosing:

A dose of 100 mg (ie, 1.0 mL) nirsevimab will be obtained by withdrawing the entire contents of 2 investigational product vials with an appropriately sized syringe and administered as 1 single (ie, 1.0 mL) injection.

2. Children in the second year of life and entering their second RSV season at time of dosing

A dose of 200 mg (ie, 2.0 mL) nirsevimab will be obtained by withdrawing the entire contents of 4 investigational product vials with an appropriately sized syringe and administered as 2 injections (1.0 mL each).

3. Switch the needle prior to administration.
4. Nirsevimab should be administered in the anterolateral aspect of the thigh according to standard practice procedures for IM injections. The injection should be given using standard aseptic technique. Subjects receiving the 200-mg dose (administered as 2 injections) should receive 1 injection in each thigh. The maximum volume to be administered with each injection is 1.0 mL.
5. Nirsevimab should be administered using the appropriate size needle ranging from 22 to 25 gauge and 5/8 to 1.0 inches based on muscle size and weight of the subject.

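### Does dropping RSV season from dose selection in SAP 1.2, against the protocol's joint age-and-season rule, leave the analysis of mismatched children undefined?

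*SAP*

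**What the plan says.** SAP 1.2 opens its dosing description with "Due to atypical RSV circulation and RSV seasons in 2020/2021, the RSV season will not be" considered for dose selection. It then says "The dose of nirsevimab is administered only based on the age and body weight regardless of the first or second RSV season" applies. A child in the first year of life falls under the 50 mg or 100 mg rule by weight, and a child in the second year under the 200 mg rule.

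The global protocol (Amendment 3) joins the two conditions in three places:

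- Section 3.1.2 reserves the 200 mg regimen for "Subjects in their second year of life AND entering their second RSV season at the time of dose administration".
- Inclusion criterion 1 in Section 4.1.2 covers children up to 24 "months of age who, per Investigator judgment, are" either in the first year and first season or "In their second year of life AND entering their second RSV season at the time of dose administration".
- Section 4.5.1.2 labels the 200 mg preparation step "Children in the second year of life and entering their second RSV season at time of dosing".

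The synopsis and Section 3.1.1 describe the dose groups by season alone. Section 4.1.4 adds that "Subjects who fail to meet the inclusion/exclusion criteria (ie, screening failures) should not receive investigational product". Section 4.1.6 withholds product from a child who "failed to meet all of the inclusion criteria for study participation".

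SAP Section 1 says that changes to protocol specifications will be described in SAP Section 6. That section has two entries: the unplanned interim analysis and the PK summary rules.

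**The concern.** On their face, the documents give different answers on whether, and with which dose, a child is treated when year of life and season disagree. The SAP gives atypical seasons as its reason, so such children were evidently thought possible. A reader who goes to SAP Section 6 for departures from the protocol will not find this one. Protocol 7.5 asks for a protocol amendment when study procedures change, and the supplied global protocol contains none for this.

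If children had been dosed outside inclusion criterion 1 with no stated way of classifying them, the analysis set or the dose groups might be ambiguous. A reader might also be unable to tell how many children were affected.

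**Working it through.** No arithmetic applies: the study has no formal comparisons (SAP Section 4), so no power or error rate is involved. The check has two parts. The first is which children the wordings treat differently. The second is what the SAP does with their data.

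**Where the wordings diverge**

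| Year of life | RSV season entered | SAP 1.2 | Protocol 3.1.2, 4.1.2, 4.5.1.2 | Synopsis and 3.1.1, read alone |
|---|---|---|---|---|
| First | First | 50/100 mg by weight | 50/100 mg by weight | 50/100 mg by weight |
| Second | Second | 200 mg | 200 mg | 200 mg |
| Second | First | 200 mg | not eligible | 50/100 mg by weight |
| First | Second | 50/100 mg by weight | not eligible | 200 mg |

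The first two rows agree throughout. The conflict is confined to the last two, and a child reaches those rows only if the investigator judges criterion 1 not met. The number is not given; its lower bound is 0.

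**What the SAP does with a child in either of the last two rows, once dosed**

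1. Analysis set: SAP 2.1 puts every enrolled subject who received any nirsevimab in the as-treated population. The child is in.
2. Eligibility failure: SAP 2.2 keeps enrolled but ineligible subjects in that set and plans no per-protocol analysis. The child stays in, whatever label is given.
3. Dose column: SAP 4.1 presents data by dose actually administered (50/100 mg, 200 mg, total). The child's column follows from the dosing record and needs no season.
4. ADA: the median of maximum titers in SAP 4.2.5.2 is taken within the same actual-dose groups.
5. PK: SAP 4.2.5.1 summarises concentrations by dose and by immunocompromising condition. Season does not enter.
6. Age and weight: SAP 4.2.2 tabulates age under 12 months against 12 months or more, and weight category. With the dose columns of SAP 4.1, a reader can see whether dosing followed the age rule in SAP 1.2.

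None of these steps needs a further rule for a mismatched child. What is not stated is whether the mismatch is reported as an eligibility failure or an important protocol deviation. SAP 2.2.1 refers deviation details to the Protocol Deviation Management Plan, which is not among the documents, and SAP 4.2.1 provides an eligibility summary.

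**Disclosure**

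Of the 2 entries in SAP Section 6, 0 concern season. The change does appear with its reason in SAP 1.2, and the SAP amendment history logs it with reference to a note-to-file. The same history logs the removal of season from the baseline summary and from the subgroup analyses. The entry is therefore in the wrong place rather than withheld.

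**The case for a change.** The strongest case for acting is that the SAP breaks its own promise. Section 1 covers any change to a protocol specification, not only changes of analysis, and Section 6 was being kept up to date, since both its entries match items in SAP Amendment 3. Protocol 7.5 calls for an amendment, and inclusion criterion 1 was itself revised by protocol Amendment 2. The remedy looks cheap: a Section 6 entry, a sentence on classification, and a count of mismatches by dose group.

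The facts stand. A Section 6 entry was owed, and the supplied global protocol does not reflect the rule in SAP 1.2. The Japan amendment and the note-to-file are not available, so nothing can be said about what they contain.

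The inference to a change in the plan does not stand. A Section 6 entry would repeat what SAP 1.2 already says. A classification sentence would alter a label and leave every analysis set as it is. A count would need a defined season for each child, when the SAP's reason for dropping season is that seasons were atypical, and neither the protocol's procedure schedules (Tables 4 and 5) nor Section 4.3.2 lists season as an item to collect. SAP 5.2 already plans an analysis once globally enrolled subjects have reached Day 151, so an amendment now may only document dosing that has taken place.

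**Conclusion.** No change to the statistical plan is called for. The protocol and SAP passages on dose selection contradict each other for children whose year of life and season disagree, and the sponsor's clinical team must reconcile them; no view is taken here on which rule is right. That is a matter of record. It leaves no analysis undefined, because set membership and dose column are fixed by SAP 2.1, 2.2 and 4.1 for every dosed child.

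The size is an unknown number of children, possibly zero, out of about 100 planned, with no test affected and no planned summary that would be computed differently. This rests on two assumptions: that dose actually given is recorded for each child, as SAP 4.1 requires, and that the deviation plan or the eligibility summary handles the remaining label in the usual way. If the second fails, a reader loses a descriptive count but no estimate changes.

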**Figure 1 Study Flow Diagram**

IM = intramuscular; LRTI = lower respiratory tract infection; n = number of subjects; RSV = respiratory syncytial virus.

### 1.3 Number of subjects

A total of approximately 100 subjects are planned to receive a single IM dose of nirsevimab to evaluate the safety, PK, ADA, and efficacy, which will be assessed descriptively. The original proposed sample size, as stated in the original CSP dated 27 January 2020, was based on a similarly designed palivizumab study in a similar population (Mori, et al. 2014), and it is expected to be sufficient in establishing a PK profile that allows extrapolation of efficacy and safety data from the Phase 2b (D5290C00003) and Phase 3 (CCI [REDACTED]) studies in healthy preterm and term infants to the target immunocompromised population. The updated sample size of 100, from the original sample size of 30 as stated in the original CSP, allows for the collection of PK and safety data from a larger cohort of immunocompromised children, and for the study of immunocompromised children and the various causes for this condition globally. Further, the data from this study will support the evaluation of safety in a diverse population, which could potentially facilitate the examination of subpopulations.

CCI  
[REDACTED]

Subjects will not be replaced.

## 2 ANALYSIS SETS

### 2.1 Definition of analysis set

The analysis sets defined in this study are the as-treated population and the as-treated Japan subpopulation. All analyses performed are to be conducted on these populations unless stated otherwise.

The as-treated population includes all subjects who are enrolled (once written informed consent is obtained) and received any dose of nirsevimab.

The as-treated Japan subpopulation is a subset of the as-treated population and includes only subjects who were enrolled in sites located in Japan.

### 2.2 Violations and deviations

Subjects who do not meet eligibility criteria but are still enrolled will be analyzed according to the analysis set described in Section 2.1. There is no intention to perform a per-protocol analysis in this study.

### **2.2.1      Important protocol deviations**

Important protocol deviations (IPDs) are a subset of protocol deviations that may significantly impact the completeness, accuracy and/or reliability of the study data or that may significantly affect a subject's rights, safety, or well-being.

Only important protocol deviations will be summarized and listed in the clinical study report (CSR). The number and percentage of subjects with at least one IPD will be summarized by the categorization of protocol deviations. The number and percentage of subjects whose IPDs are related to COVID-19 will also be provided. A list of IPDs will be reviewed and finalized by the medical advisors and statisticians prior to database lock. Full details are described in the Protocol Deviation Management Plan.

## **3            PRIMARY, SECONDARY AND EXPLORATORY VARIABLES**

### **3.1        Primary variables**

The following safety data will be collected: treatment-emergent adverse events (TEAEs), treatment-emergent serious adverse events (TESAEs), adverse events of special interest (AESIs), skin reactions, and new onset chronic diseases (NOCDs).

Adverse events and serious adverse events (SAEs) will be collected from the time of signature of informed consent through Day 361. Adverse events of special interest and NOCDs will be collected from the time of dosing through Day 361. Adverse events will be coded using the latest version of the Medical Dictionary for Regulatory Activities (MedDRA), Version 24.1 or higher.

#### **3.1.1      Treatment-emergent adverse events and serious treatment-emergent adverse events (TEAEs and TESAEs)**

Treatment-emergent adverse events are defined as AEs whose onset occurs after receiving nirsevimab and within 360 days post dose. Adverse events with completely missing onset dates and a stop date after the start date of receiving nirsevimab (or unknown stop date) will also be considered treatment emergent. A TESAE is an TEAE which is serious.

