5 ASSESSMENT OF SAFETY

5.1 Definition of Adverse Events

An AE is the development of any untoward medical occurrence in a subject or clinical study subject administered a medicinal product and which does not necessarily have a causal relationship with this treatment. An AE can therefore be any unfavorable and unintended sign (eg, an abnormal laboratory finding if judged by the Investigator as medically significant), symptom (eg, nausea, chest pain), or disease temporally associated with the use of a medicinal product, whether or not considered related to the medicinal product.

The term AE is used to include both serious and nonserious AEs and can include a deterioration of a pre-existing medical occurrence. An AE may occur at any time, including run-in or washout periods, even if no investigational product has been administered.

Elective treatment or surgery or preplanned treatment or surgery (that was scheduled prior to the subject being enrolled into the study) for a documented pre-existing condition that did not worsen from baseline is not considered an AE (serious or nonserious). An untoward medical event occurring during the prescheduled elective procedure or routinely scheduled treatment should be recorded as an AE or SAE.

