5.5 Recording of Adverse Events

AEs, including SAEs, AESIs, and NOCDs, will be recorded on the eCRF using a recognized medical term or diagnosis that accurately reflects the event. These events will be assessed by

the Investigator for severity, relationship to the investigational product and study procedure(s), possible etiologies, and whether the event meets criteria of an SAE (see Sections [5.2](#) and [5.6](#)), or is an AESI or NOCD (see Sections [5.3](#), [5.4](#), and [5.7](#)) and therefore requires immediate notification to the Sponsor. See [Appendix A](#) for guidelines for assessment of severity and relationship to investigational product.

If an AE evolves into a condition that meets the regulatory definition of “serious,” it will be reported on the AE form in the eCRF as an SAE.

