5.5.1 Time Period for Collection of Adverse Events

AEs and SAEs will be collected from the time of signature of informed consent through Day 361.

AESIs and NOCDs will be collected from the time of dosing through Day 361.

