The number and percentage of subjects with TEAEs with outcome of death, as well as categorization by MedDRA SOC and PT will be provided. Key information similar to those mentioned above will be listed for subjects with outcome of death.

Non-treatment-emergent AEs/ SAEs, defined as AEs/SAEs that occur prior to administration of nirsevimab or after Day 361, will be presented in an AE listing.

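### SAP 3.1.1 defines treatment-emergent events by onset date alone, so an AE first recorded between consent and dosing that worsens after nirsevimab can be missing from the primary safety and death tables

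*SAP*

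**What the plan says.** - **Definition.** SAP 3.1.1: "Treatment-emergent adverse events are defined as AEs whose onset occurs after receiving nirsevimab and within 360 days post dose". Seriousness is added on top: "A TESAE is an TEAE which is serious". The one exception to the onset rule in that section is for "Adverse events with completely missing onset dates and a stop date after the start date of receiving nirsevimab" (or an unknown stop date). It deals with missing dates, not with worsening.
- **Collection.** Protocol 5.5.1: "AEs and SAEs will be collected from the time of signature of informed consent through Day 361". Screening runs from Day -30 to Day -1 (Protocol Table 4) and may fall on the dosing day (Table 5, note a).
- **Tables.** SAP 4.2.4.1 builds the overall, serious, Grade 3 or higher and related rows from TEAEs and TESAEs. Deaths are tabulated as "The number and percentage of subjects with TEAEs with outcome of death". Grade, seriousness and fatal outcome are all read from the same AE page of the eCRF.
- **Everything else.** SAP 4.2.4.1 treats the remaining events as non-treatment-emergent, "defined as AEs/SAEs that occur prior to administration of nirsevimab or after Day 361, will be presented in an AE listing".
- **Recording of worsening.** Protocol 5.1 says an AE "can include a deterioration of a pre-existing medical occurrence". Protocol 5.5 says of an AE that evolves to meet the serious criteria that "it will be reported on the AE form in the eCRF as an SAE". Neither says whether the existing record is upgraded or a new one is opened, or which onset date applies.

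**The concern.** TEAEs and TESAEs are the primary endpoint, the trial has no control arm, and the analysis is descriptive, so the tabulated counts are the result. Under an onset-only rule, a post-dose change in grade, seriousness or outcome plays no part in classification. If a site upgrades an AE that began in screening, the record carries its final grade and outcome together with a pre-dose onset date, and the primary tables skip it. The error can only lower the counts. It would fall on children who were already unwell at dosing, in a population that includes transplant recipients and children on chemotherapy or other immunosuppression. A death following such an AE would be absent from the only death table planned.

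**Working it through.** The plan has no figure of its own to reproduce: there is no power calculation and no assumed rate of screening AEs. The check is a trace of the rules, followed by a sense of scale.

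**1. One clinical course, three ways of recording it (hypothetical).** A child has a Grade 2 event, is dosed on Day 1, and the event is Grade 4 and serious on Day 10.

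| Recording | Onset on the record | TEAE, TESAE and Grade 3+ rows | If fatal: fatal-TEAE table |
|---|---|---|---|
| AE first recorded Day -10, same record upgraded | Day -10 | No; listing only | No |
| AE first recorded Day -10, new record opened for the worsening | Day 10 | Yes | Yes |
| Condition already present at consent, deterioration recorded as an AE (Protocol 5.1) | Day 10 | Yes | Yes |

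The first two rows differ only in a recording choice that neither document settles. The third shows that conditions already present at consent can enter the tables when they deteriorate. The gap is therefore confined to AEs that arise between consent and dosing.

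**2. Size per event.** Inputs: about 100 children in all and about 50 per dose group (Protocol 3.1.1). One event is 1/100 = 1.0 percentage point overall, or 1/50 = 2.0 points in a dose group. The SAP plans no intervals for these rows; exact 95% limits are used here only as a scale. With no events the upper limit is 1 − 0.025^(1/n). With x events it is the 97.5th percentile of Beta(x + 1, n − x).

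| Count | Upper limit |
|---|---|
| 0/100 | 3.6% |
| 1/100 | 5.4% |
| 2/100 | 7.0% |
| 0/50 | 7.1% |
| 1/50 | 10.6% |

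**3. Chance that it matters at all.** The rate p of affected children is an assumption. The probability of at least one in 100 is 1 − (1 − p)^100.

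| Assumed p | Expected children | P(at least one) |
|---|---|---|
| 0.5% | 0.5 | 39% |
| 1% | 1 | 63% |
| 2% | 2 | 87% |
| 5% | 5 | 99% |

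**4. Effect by row.** A child missing from one row may already be counted there for another event. The only large infant rates in the documents are from the Phase 2b study in healthy preterm infants (Protocol 1.4.3): 86.2% with any TEAE and 11.2% with a TESAE on nirsevimab. These are illustrative only, and independence is assumed.

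- Any-TEAE row, 1 child: (1 − 0.862) × 1/100 = 0.14 points.
- Any-TEAE row, 6 children: (1 − 0.862) × 6/100 = 0.83 points. Six is a generous assumption: 30% of 100 children with an AE ongoing at dosing, 20% of whom worsen (100 × 0.30 × 0.20 = 6). With 10% and 10% it is 1.
- TESAE row, 1 child: (1 − 0.112) × 1/100 = 0.89 points.

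The common row absorbs the loss. The rarer rows do not.

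**The case against.** The strongest reply is that the loss is conditional. Protocol 5.1 allows a deterioration to be an AE, and one entered with a Day 10 onset is a TEAE under the SAP as written. Protocol 5.5 is silent on onset date, and the eCRF instructions and Data Management Plan mentioned in Protocol 6.4 may settle the matter; they are not available here. Protocol Appendix A describes non-treatment-emergent SAEs as those occurring before dosing, which does not clearly describe an event that became serious afterwards. All of this stands, and it limits the point to a rule that can miscount, depending on site practice.

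The exposed group is also narrow. Screening and dosing may be on the same day. Exclusion criteria 3 and 4 remove active infection and recent fever or acute illness, and criteria 5, 11 and 12 narrow the group further. They do not expressly remove drug toxicities or non-infectious transplant complications that first appear in screening.

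Nor are the events hidden. They are listed, every death is reported as an SAE (Protocol 5.5.3), discontinuations are summarised, the data monitoring committee reviews safety, and no decision rule depends on the tables. True, but a listing does not correct a percentage in a primary table.

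A reader might infer two stronger things. One is that the AESI tables lose events in the same way. The documents give little support for that: AESIs are collected only from dosing (Protocol 5.5.1), thrombocytopenia calls for expedited reporting only when unexpected, clinically significant and of unknown cause (Protocol 5.7.3.3), and primary interpretation rests on investigator assessment (SAP 4.2.4.2). A known chemotherapy cytopenia would at most affect the supplementary term-based analysis. The other is that TEAE incidence is understated by several percentage points. That needs rates the documents do not give, and even six affected children would barely move the any-TEAE row.

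**Conclusion.** The point holds in a limited form. SAP 3.1.1 classifies by onset alone, SAP 4.2.4.1 sends pre-dose AEs to a listing and restricts the death table to fatal TEAEs, and neither document has a worsening clause. An AE that arises between consent and dosing, keeps its record and then becomes severe, serious or fatal after nirsevimab is left out of the primary safety tables. Whether this happens depends on site recording practice, which the documents leave open. They do not support saying that such events are always lost.

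The number of children is unknown and probably small. The effect lies in the preferred-term, Grade 3 or higher, serious and fatal rows, at up to 1 percentage point per child in 100. It is clearest for deaths, where one case separates 0/100 from 1/100. It is minor for the any-TEAE row. Because the counts are the primary result of an uncontrolled study and the remedy is cheap, it is worth correcting before the final database lock.

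**What to change.** 1. **SAP 3.1.1.** Add to the TEAE definition any AE with onset before dosing that increases in severity, becomes serious or becomes fatal after dosing, through 360 days post dose. TESAEs then follow. State that if the worsening was also entered as a separate record, the event is counted once; without this the new limb could double-count.
2. **SAP 4.2.4.1.** Next to the fatal-TEAE table, tabulate all deaths after dosing through Day 361 regardless of AE onset date, and adjust the wording on non-treatment-emergent events to match.
3. **SAP 4.2.4.5.** State that the onset-time subgroups use the date of worsening for these events. Otherwise a negative study day would satisfy every category, including study day 1 or earlier.
4. **Data.** No retrospective change to eCRF recording is needed. Review the few pre-dose AEs still ongoing at dosing and establish whether and when each worsened.

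The cost is a few lines of SAP text, one table, a little programming and a short case review. TEAE and TESAE counts may become slightly less favourable and may differ from the interim outputs, which should be footnoted.
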